#### Appendix 3 - Effectiveness of family planning methods

https://www.cdc.gov/reproductivehealth/unintendedpregnancy/pdf/contraceptive methods 508.pdf

**U.S. Department of** CDC **Health and Human Services** Centers for Disease Control and Prevention

Emergency Contraception: Emergency contraceptive pills or a copper IUD after unprotected

intercourse substantially reduces risk of pregnancy.

Adapted from World Health Organization (WHO) Department of Reproductive Health and Research, Johns Hopkins Bloomberg School of Public Health/Center for Communication Programs (CCP). Knowledge for health project. Family planning: a global handbook for providers (2011 update). Baltimore, MD; Geneva, Switzerland: CCP and WHO; 2011; and Trussell J. Contraceptive failure in the United States. Contraception 2011;83:397–404.

1 BACKGROUND

This is a phase 1/2a, open label, multicenter, multi dose, dose escalation trial of VK-2019, a potent and selective inhibitor of the EBV latency program through its specific binding to a viral target, EBNA1, in patients with Epstein Barr Virus positive nasopharyngeal cancer, with pharmacokinetic (PK), and pharmacodynamics (PD) correlative studies.

This statistical analysis plan (SAP) is for the abbreviated CSR of study VK-2019-001 and is based on the approved clinical study protocol, 15 October 2019, Version 9.0, Amendment 9.

The purpose of this document is to provide details about the statistical analysis methods for the VK-2019-001 protocol "Phase 1/2a open label, multicenter clinical trial of a novel small molecule EBNA1 inhibitor, VK-2019, in patients with Epstein Barr Virus positive nasopharyngeal cancer, with pharmacokinetic and pharmacodynamic correlative studies".

For background of study refer to Protocol Section 2 Background.

2 STUDY DESCRIPTION

[figure not shown]
2.1 Study Design

This is a phase 1/2a, open label, multicenter, multi dose, dose escalation trial of VK-2019, a potent and selective inhibitor of the EBV latency program through its specific binding to a viral target, EBNA1.

For each patient enrolled, the study will consist of at least three periods: Screening (up to 28 days), Treatment (comprised of 28-day dosing cycles), and Follow up (comprised of a safety follow-up and long-term follow-up for survival status).

This trial is divided into three parts (Figure 1): Phase 1 Dose Escalation, Phase 1 Dose Expansion, and Phase 2a Dose Expansion. One sub-study, collecting tumor biopsies, will be conducted during the Phase 2 Expansion part of the trial.

Figure 1: Study Design Schema

Note: Three Phase 1 and two Phase 2 dose expansions are not specifically planned. The total number of expansions opened will depend upon biological and clinical activity observed in the trial

2.1.1 Phase 1 Dose Escalation

Dose escalation in this trial will be conducted utilizing both an accelerated titration, based in part upon a 3B design proposed by Simon et al (1), coupled with a "rolling six" design (2). Five dose escalation cohorts are planned, but additional dose escalation or intermediate de-escalation cohorts may be explored based upon emerging safety and/or PK data.

By utilizing these designs it is expected to maximize accrual at pharmacologically relevant doses, both by potentially minimizing accrual at subtherapeutic dose levels and more efficiently establishing an understanding of the safety profile of VK-2019 (3).

Dose escalation will initially proceed according to the accelerated titration design, enrolling one new patient per dose level. Upon any instance of a VK-2019 related Grade \geq 2 AE during Cycle 1, dose escalation will convert to the Rolling Six design in which 3-6 patients per dose level will be enrolled.

2.1.2 Phase 1 Dose Expansion

During dose escalation, one or more cohorts may be selected for expansion, enrolling up to 16 patients (inclusive of the patients already enrolled at the same dose during escalation) at any dose level that is assessed to either be the MTD or have sufficient activity to meet criteria as a BCAD.

2.1.3 Phase 2a Dose Expansion

Further dose expansion in the Phase 2a part of the trial may be explored by utilizing the Simon 2 Stage design. Up to an additional nine patients may be enrolled at a particular dose if two or more objective responses (at least one must be confirmed) are observed out of 16 patients at that dose in the Phase 1 part of the trial (for a total accrual of up to 25 patients). See Protocol Section 6 for details on initiating a Phase 2a Dose Expansion.

2.2 Treatment Assignment

The starting dose for VK-2019 is 60 mg QD. Sample dose escalation tables are below in Table 1, detailing a sample dose escalation schema based upon when escalation converts from Accelerated Titration to a Rolling Six design.

2.2.1 Definition of a Completed Cohort and an Evaluable Patient

Each dose escalation cohort will consist of either:

- 1 evaluable patient (Accelerated Titration cohorts), or
- 3-6 evaluable patients (Rolling Six cohorts)

To be considered evaluable, a patient will have and one of the following:

[figure not shown]
- Received 75% of doses during Cycle 1, or,
- Received at least one dose of VK-2019 and experienced a DLT during Cycle 1

2.2.2 Dose Escalation in Accelerated Titration Cohorts

Upon completion of an accelerated titration cohort (Figure 2):

- IF: No VK-2019 related Grade ≥ 2 AEs occur during Cycle 1; THEN: Dose escalation may proceed to the next accelerated titration cohort (no greater than a 100% dose increase).
- IF: The patient experiences any VK-2019 related Grade ≥ 2 AE during Cycle 1 (not meeting the definition of a DLT); THEN: Convert the current cohort to the Rolling Six design, and enroll an additional 2-5 patients (3-6 total).
- IF: The patient experiences a DLT;THEN: Convert to the Rolling Six design and enroll an additional five patients (six total).

Figure 2: Accelerated Titration Dose Escalation Schema

2.2.3 Dose Escalation in Rolling Six Cohorts

Upon completion of a Rolling Six cohort (a minimum of three, maximum of six evaluable patients), if:

- 0 of 3 patients experience a DLT; dose escalation may proceed to the next cohort (no greater than a 50% dose increase)
- 1 of 3 patients experience a DLT; an additional three evaluable patients will be enrolled into the cohort
- ≤ 1 of 6 patients experience a DLT; dose escalation may proceed to the next cohort (no greater than a 50% dose increase)

• ≥ 2 patients experience a DLT; the MTD has been exceeded and further enrollment into that cohort will cease. Lower-dose cohorts may then be explored until the MTD has been determined, including intermediate doses.

Dose Escalation Schema	Target Dose / Actual Dose	Dose Increase
	60 mg / 60 mg	n/a
All asherts appelled using Assoluted	120 mg / 120 mg	100%
All cohorts enrolled using Accelerated Titration	240 mg / 230 mg	100%
	460 mg / 460 mg	100%
	920 mg / 920 mg	100%
	60 mg / 60 mg	n/a
Polling six annullment begins at the	90 mg / 90 mg	50%
Rolling-six enrollment begins at the 60 mg cohort	135 mg / 120 mg	50%
oo mg conon	180 mg / 180 mg	50%
	270 mg / 260 mg	50%
	60 mg / 60 mg	n/a
Dolling giv appellment beging at the	120 mg / 120 mg	100%
Rolling-six enrollment begins at the 120 mg cohort	180 mg / 180 mg	50%
	270 mg / 260 mg	50%
	390 mg / 380 mg	50%
	60 mg / 60 mg	n/a
Dalling air annallmant haging at the	120 mg / 120 mg	100%
Rolling-six enrollment begins at the 230 mg cohort	240 mg / 230 mg	100%
	345 mg / 320 mg	50%
	480 mg / 460 mg	50%
	60 mg / 60 mg	n/a
Delling air annollment hearing of the	120 mg / 120 mg	100%
Rolling-six enrollment begins at the	240 mg / 230 mg	100%
460 mg cohort	460 mg / 460 mg	100%
	690 mg / 690 mg	50%

Note: Sample dose levels are based upon dose escalation (target dose) and available VK-2019 capsule strengths of 30 and 200 mg (actual dose).

2.2.4 Intra-Patient Dose Escalation in Accelerated Titration Cohorts

After an accelerated titration cohort has been declared safety by the SRC, patients at lower dose levels may be considered for intra-patient dose escalation if they meet the following criteria based in part on 3B design proposed by Simon et al:

• Have stable disease (SD) or better after Cycle 2 (or later)

- Experienced no VK-2019 related Grade 2 AEs during the previous cycle
- Have no other safety concerns as assessed by the inverstigator

The escalated dose must be agreed upon by the investigator and sponsor and may proceed beginning on Day 0 of the next cycle. Any patient that has their dose escalated will not be evaluated for DLT assessment at their new dose.

2.2.5 Intra-Patient Dose Escalation in Rolling Six Cohorts

After a Rolling Six cohort has enrolled a minimum of three patients and has been declared safe by the SRC, patients at lower dose levels may be considered for intra-patient dose escalation if the patient meets the following criteria:

- Have stable disease (SD) or better after Cycle 2 (or later)
- Have no other safety concerns as assessed by the investigator

The escalated dose must be agreed upon by the investigator and sponsor and may proceed beginning on Day 0 of the next cycle. Any patient that has their dose escalated will not be evaluated for DLT assessment at their new dose.

2.3 Blinding and Unblinding

This is an open-label study and there will be no blinding of subjects' treatment during this study.

2.4 Protocol Amendments

This analysis plan reflects revised protocol version 09, amendment 9, and dated 15-OCTOBER-2019.

3 OBJECTIVES

3.1 Primary

Phase 1:

- To define the MTD and the RP2D for orally administered VK-2019 monotherapy in patients with recurrent or metastatic NPC.
- To evaluate and characterize the safety profile of single agent VK-2019 in adult patients with recurrent or metastatic NPC.

Phase 2a:

- Evaluate preliminary efficacy (ORR, DOR, DCR, PFS, survival rate, and OS) of orally administered VK-2019 monotherapy in adult patients with recurrent or metastatic NPC.
- Confirm the safety and tolerability of orally administered VK-2019 monotherapy in adult patients with recurrent or metastatic NPC.

3.2 Secondary

Phase 1:

- To evaluate the anti tumor activity of single agent VK-2019 per RECIST v1.1.
- To characterize the single dose and steady state pharmacokinetic profile of single agent VK-2019 in adult patients with recurrent or metastatic NPC.
- To evaluate the anti-EBV activity by reduction of plasma EBV-DNA of single agent VK-2019 in adult patients with recurrent or metastatic NPC.

Phase 2a:

- To further characterize select PK parameters associated with orally administered VK-2019 monotherapy in adult patients with recurrent or metastatic NPC.
- Evaluate the anti EBV activity by reduction of plasma EBV DNA of orally administered VK 2019 monotherapy in adult patients with recurrent or metastatic NPC.

3.3 Exploratory

Phase 1:

- To explore blood PD markers.
- To explore PD markers such as alteration in EBV specific gene expression, both lytic and latent EBV genes.
- To explore exposure response relationships between VK 2019 exposure and the PD endpoints (safety, efficacy, and laboratory correlatives).

Phase 2a:

- To explore both blood and intratumoral PD markers.
- To explore PD markers such as alteration in EBV specific gene expression, both lytic and latent EBV genes.

• To explore exposure response relationships between VK 2019 exposure and the PD endpoints (safety, efficacy, and laboratory correlatives).

4 ENDPOINTS

4.1 **Primary Endpoints**

Phase 1:

• The frequency, severity, and duration of AEs and DLTs, AEs leading to discontinuation. and AEs leading to death.

Phase 2a:

• The durable ORR rate as well as ORR, DOR, DCR-6, DCR-12, PFS, rate of survival, and OS per RECIST v1.1.

4.2 Secondary Endpoints

Phase 1:

- The rate and severity of treatment emergent AEs at the MTD and BCAD.
- Single dose and steady state plasma pharmacokinetic parameters of VK 2019.
- Incidence of safety laboratory assessment abnormalities
- Incidence of abnormalities in vital signs or other clinical safety assessments
- ORR, DOR, and Disease control rate (DCR) per RECIST v1.1
- Rate of partial or complete plasma EBV DNA antiviral response during treatment (assessed as 3xlog¹⁰ reduction or a drop below the lower limit of detection of the assay [LLOD], respectively).

Phase 2a:

- The rate and severity of treatment emergent AEs at the MTD, BCAD, and RP2D.
- Rate of partial or complete plasma EBV DNA antiviral response during treatment (assessed as 3xlog¹⁰ reduction or a drop below the lower limit of detection of the assay [LLOD], respectively).
- Plasma PK parameters of VK-2019.

4.3 Exploratory Endpoints

Phase 1:

• Exploratory analysis of relationships among PK, PD and clinical activity in order to preliminarily define BCAD.

Phase 2a:

• Exploratory PD assay for EBER in situ hybridization levels in baseline and on treatment tumor biopsies in a limited number of patients at RP2D.

5 SAMPLE SIZE AND POWER

The number of patients in the dose escalation phase is estimated to be 30 patients (assuming six patients will be dosed in each of five cohorts). The number of patients in the Phase 1 Dose Expansion and Phase 2a Dose Expansion is based on a Simon 2-stage design as described below. The approximate sample size in the Phase 1 Dose Expansion is estimated to be 20 patients (assuming 10 additional patients in each of two expanded dose levels). During the Phase 2a portion of the trial, the approximate sample size in the Phase 2a Dose Expansions is estimated to be 18 (assuming 9 patients in each of two expansion cohorts). In total, it is estimated that up to approximately 68 patients will be dosed in this trial.

The number of patients for the Phase 1 and 2a expansions is based upon a Simon Two-Stage design at BCAD and MTD, respectively. The null hypothesis that the true response rate is 0.1 will be tested against a one-sided alternative. In the first stage (i.e., a Phase 1 Dose Expansion cohort), a total of 16 patients will be accrued. If there is one or fewer responses in these 16 patients, accrual to this cohort will be stopped. Otherwise, 9 additional patients will be accrued (i.e., a Phase 2a Dose Expansion cohort) for a total of 25. The null hypothesis will be rejected if five or more responses are observed in 25 patients. This design yields a 1-sided type I error rate of 10% and power of 90% when the true response rate is 30%. This design yields a probability of 0.51 for a cohort stopping early if the true response rate for that cohort is 10%. The sample size in the dose escalation phase is not based on statistical considerations, but rather depends on the number of observed toxicities; up to 6 subjects are expected to be treated after the accelerated titration design has ended at each conventional escalation cohort dose prior to the expansion cohort at MTD.

6 STUDY PERIODS, DOSAGE AND ADMINISTRATION

6.1 Study Periods

For each patient enrolled, the study will consist of at least three periods: Screening (up to 28 days), Treatment (comprised of 28-day dosing cycles), and Follow up (comprised of a safety follow-up and long-term follow-up for survival status).

6.1.1 Safety Follow-Up

A safety follow up visit will be conducted at least 28 days (\pm 7 days) after the patient's last dose of study drug.

6.1.2 Long-Term Follow-Up

All patients that discontinue study treatment will be followed for:

- Survival: Via clinic visit (either at the study site or outside facility), telephone, or videotelephony until a) death, b) withdrawal of consent, c) they are lost to follow-up, d) the Sponsor notifies sites that survival follow-up is no longer required, or e) termination of study by the Sponsor, and
- Assessment of treatment-related SAEs until resolution to baseline or Grade ≤ 1 .

Patients discontinuing treatment due to reasons other than radiographic disease progression will have their tumor assessed (using the same modality that was used during study treatment) every 12 weeks (\pm 14 days) for up to 2 years after the last treatment visit, or until a) they have progressive disease, b) they start a new therapy for their cancer, b) death, c) withdrawal of consent, d) they are lost to follow-up, e) the Sponsor notifies sites that tumor assessment is no longer required during long-term follow-up, or f) termination of study by the Sponsor.

6.2 Dosage and Administration

The number of patients in the dose escalation phase is estimated to be 30 patients (assuming six patients will be dosed in each of five cohorts). The starting dose for VK-2019 is 60 mg QD. Sample dose escalation tables are in Table 1, detailing a sample dose escalation schema based upon when escalation converts from Accelerated Titration to a Rolling Six design.

VK-2019 will be provided in HDPE bottles containing either 30 mg or 200 mg capsules with protection from moisture. Patients should be given sufficient supply to last until their next study visit or for an entire cycle, depending upon institutional policy and study team discretion.

Site personnel must ensure that patients clearly understand the directions for self medication. Patients should record daily administration of each study drug in their patient diaries. If a patient misses a dose, they must be instructed not to "make it up" or double the dose on the next day. Patient diaries and pill counts by research staff at least once each cycle will be used to determine actual dosing.

If a patient vomits any time after taking a dose, they must be instructed not to "make it up," but to resume subsequent doses the next day as prescribed.

7 STATISTICAL ANALYSES

7.1 General Methods

The statistical analysis will be conducted following the principles specified in the International Conference on Harmonisation (ICH) Topic E9 Statistical Principles for Clinical Trials (CPMP/ICH/363/96).

All statistical tabulations and analyses will be done using SAS®, Version 9.4 or higher.

Unless otherwise noted, continuous variables will be summarized using number of non-missing observations (n), arithmetic mean (mean), standard deviation (SD), median, minimum, and maximum; categorical variables will be summarized using the frequency count and the percentage of subjects in each category.

In the data listings, study day relative to first dose of study drug may be presented. Study day relative to first dose will be calculated as: event date – first dose date in the study (+ 1 if event date \geq first dose date in the study).

When appropriate, baseline is defined as the last non-missing result with a collection date-time less than the date-time of the first dose of study medication. If time is missing, unless otherwise specified, baseline is the last non-missing result prior to or equal to the date of first dose of study drug.

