- 15 After completing 13 cycles of treatment (i.e., > 12 months), the Investigator and Sponsor may agree that a patient will require study visits on an every odd cycle basis only (i.e., C15D0, C17D0, C19D0, etc.), until more frequent visits become clinically indicated.
- 16 Visits performed out of window due to holidays, natural disasters, and similar circumstances will not be a protocol deviation.

Visit	Timonoint	Assessme	ents
VISIt	Timepoint	PK Plasma	ECG
Screening	n/a		Х
C1D0	Pre-dose (-1 hour)	Х	Х
	30 mins post-dose ( $\pm 5$	Х	
	m)		
	$1 h post (\pm 10 m)^1$	Х	Х
	2 h post (± 10 m)	Х	
	3 h post (± 10 m)	Х	
	4 h post (± 10 m)	Х	
	6 h post (± 10 m)	Х	
	8 h post (± 30 m)	Х	
	24 h post (± 2 h)	Х	
C1D14	Pre-dose (-1 h)	Х	Х
	$1 h post (\pm 10 m)^1$	Х	Х
C2D0	Pre-dose (-1 h)	Х	Х
	$1 h post (\pm 10 m)^1$	Х	Х
C2D14	Pre-dose (-1 h)		
	1 h post (± 10 m)		
C3D0	Pre-dose (-1 h)	Х	
	$1 \text{ h post } (\pm 10 \text{ m})^1$	Х	
EOT	n/a		Х

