# Electrocardiograms

ECGs using a 12-lead tracing will be collected in triplicate (i.e. three 10-second tracings approximately 1 minute apart) and should be performed in the supine position unless collecting them in this position is not feasible. A machine with the capacity to calculate standard intervals automatically should be used. At each time point, heart rate and PR, R-R, QRS, and QT intervals will be calculated.

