7.14.4 Electrocardiograms

Absolute and change from baseline 12-lead ECG results will be summarized using descriptive statistics. QT analysis intervals will be corrected for heart rate using the Fridericia correction (QTcF). Study conclusions will be based on the most appropriate correction method for the

analysis. The effect of VK-2019 concentration on QTcF will be explored after dosing and will be baseline corrected for each patient.

Individual ECG data will be listed.

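### SAP 7.1's missing-time fallback can make the C1D0 1 h post-dose ECG the baseline, and the SAP neither states that triplicates are averaged nor fixes the QT correction behind its conclusions

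*SAP*

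**What the plan says.** **Baseline.** SAP 7.1 gives one definition for all assessments, to be used where appropriate: "baseline is defined as the last non-missing result with a collection date-time less than the date-time of the first dose of study medication". The fallback opens "If time is missing, unless otherwise specified" and continues "baseline is the last non-missing result prior to or equal to the date of first dose of study drug". SAP 7.14.4, the ECG section, adds no baseline definition of its own. It does plan change-from-baseline summaries and a concentration-QTcF exploration that is baseline-corrected for each patient.

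**ECG collection.** Protocol Section 11, Electrocardiograms: "ECGs using a 12-lead tracing will be collected in triplicate (i.e. three 10-second tracings approximately 1 minute apart". The same paragraph says "At each time point, heart rate and PR, R-R, QRS, and QT intervals will be calculated", without saying how three tracings become one value. The PK and ECG schedules (Protocol Tables 4 to 6) place a pre-dose and a 1 h post-dose ECG on C1D0 in all three parts of the trial.

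**Use of the mean elsewhere.** Exclusion criterion 12 applies its 470 ms QTcF limit to the mean of the screening triplicate. The toxicity table in Protocol Section 9 refers to mean QTcF. The SAP does not mention triplicates.

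**Correction.** SAP 7.14.4 names Fridericia, then adds: "Study conclusions will be based on the most appropriate correction method". Protocol Section 14.5.1, Vital Signs and 12-lead ECGs, carries the same sentence.

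**The concern.** A date-only fallback is harmless for an assessment made once, before dosing, on the first-dose date. ECGs are made on both sides of the first dose that day. A rule that includes the whole date and takes the last record can therefore pick a record made on drug. Subtracting that record removes the drug effect from the patient's 1 h change and carries the same error into every later change for that patient. Cohorts are small (1, or 3 to 6 evaluable patients), so one misassigned baseline is visible in a cohort mean.

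The other two gaps concern reproducibility. With no averaging sentence, two programmers could follow the SAP and derive different baselines from the same tracings. With the correction left open and no criterion for choosing it, the choice could be made after the QT data are known, in an open-label trial.

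**Working it through.** Neither document gives an SD, precision target or missing-time rate for QTcF, so there is no plan figure to reproduce. The variance components, effect sizes and shares below are assumptions.

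**1. When the fallback admits a post-dose ECG**

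- Dose time and 1 h ECG time both recorded: the main rule excludes the 1 h ECG because its time is after the dose.
- Dose time missing: every C1D0 ECG satisfies the date-only rule, and the last of them is the 1 h ECG.
- Time of the 1 h ECG missing: that record also satisfies the date-only rule.
- Only the pre-dose ECG time missing: applied record by record, the 1 h ECG is still excluded. Applied to the whole patient, it could be admitted. The SAP does not say which is meant.

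The fallback yields to anything specified otherwise, but SAP 7.14.4 specifies nothing.

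**2. Size of the bias**

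For an affected patient the computed 1 h change is the 1 h value minus itself, which is 0. (If one tracing is the baseline and a mean is the 1 h value, it is 0 in expectation.) At a later visit t, the computed change is Y(t) - Y(1 h) = [Y(t) - Y(pre)] - [Y(1 h) - Y(pre)], which is too low by D on average. With a share f affected, the mean reported 1 h change is D(1 - f), a bias of -f·D.

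| Assumed D (ms) | f = 5% | f = 1/6 | f = 1/3 |
|---|---|---|---|
| 5 | -0.25 | -0.83 | -1.67 |
| 10 | -0.50 | -1.67 | -3.33 |
| 20 | -1.00 | -3.33 | -6.67 |

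For example, 10 × 1/6 = 1.67. In a one-patient accelerated-titration cohort, f is 0 or 1, so an affected cohort loses all of D. With complete times f = 0 and the bias is zero.

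**3. Size of the averaging gap**

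Let s_r be the SD between tracings within a time point, and s_t the within-patient SD between time points. Take each post-dose value as a triplicate mean.

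- Single-tracing baseline: SD(change) = √(2·s_t² + s_r²·(1 + 1/3))
- Triplicate-mean baseline: SD(change) = √(2·s_t² + s_r²·(2/3))

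| Assumed s_t, s_r (ms) | Single | Mean | Ratio |
|---|---|---|---|
| 10, 3 | 14.56 | 14.35 | 1.01 |
| 5, 5 | 9.13 | 8.16 | 1.12 |
| 3, 8 | 10.17 | 7.79 | 1.31 |
| 0, 10 | 11.55 | 8.16 | 1.41 |

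Worked for 5, 5: √(50 + 33.33) = 9.13 and √(50 + 16.67) = 8.16. With six patients the standard errors are 9.13/√6 = 3.73 and 8.16/√6 = 3.33 ms.

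Over s_t from 0 to 10 and s_r from 3 to 10 ms, the increase in SD is 1% to 41%. The upper end requires s_t = 0. If post-dose values were also single tracings, the numerator becomes √(2·s_t² + 2·s_r²) and the range is 3% to 73%.

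**4. The correction**

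No arithmetic applies. The concentration analysis is fixed on QTcF in both documents; the correction behind the conclusions is not fixed in either.

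**The case against.** The strongest case against is that this is a clarification and not a demonstrated error, and several parts of it stand.

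- A reader might infer that SAP 7.1 takes the third tracing and discards the other two. The text does not say so: a result is not defined as one tracing. The protocol's time-point wording, its eligibility criterion and its toxicity table all point towards a time-point mean. What is established is that the averaging sentence is missing.
- A reader might infer that error variance is doubled. That ratio, (4/3)/(2/3) = 2, holds for replicate error alone, with no variation between time points and with averaging applied only after dosing. When the two SDs are equal, the variance ratio is 83.33/66.67 = 1.25.
- A reader might infer that the open correction makes change in QTcF noisier or lets drug effect into it. It does neither. It is a prespecification gap only.
- Contamination needs missing times. On PK days, including C1D0, dosing takes place in clinic. ECG slots are labelled, PK draws are timed from the ECG, and missing data are queried. These arrangements should make missing times uncommon, though no rate is given.
- ECG summaries are descriptive, Protocol Section 14 plans no confirmatory inference, and SAP 7.14.4 lists individual ECG data, so a reader of the listings might detect a misassigned baseline. Eligibility and toxicity management do not use the SAP baseline.

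These arguments limit the size and likelihood of the problem. They do not change what the fallback permits: no text stops a C1D0 post-dose ECG from becoming the baseline when a relevant time is missing.

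**Conclusion.** The fallback in SAP 7.1, applied as written to the C1D0 schedule, can yield an on-drug ECG baseline. The resulting bias in the cohort mean 1 h change is -f·D: -1.7 ms for an assumed 10 ms effect with one of six patients affected, and zero with complete times. Both D and f are assumptions; the documents do not show that it will happen in any patient.

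The absence of an averaging rule is a secondary gap. Its cost is an SD of change about 1% to 41% larger if single tracings were used at baseline only, and nothing if time-point means are used throughout. The open choice of correction is a third, separate gap, with no effect on the precision or bias of QTcF change itself. All three merit correction because the ECG analysis is kept in the abbreviated report and the changes are small.

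**What to change.** Add to SAP 7.14.4, overriding SAP 7.1 for ECGs:

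1. Baseline is the mean of the C1D0 triplicate identified as pre-dose by its nominal time-point label. If that triplicate is missing, use the screening triplicate mean. A record labelled post-dose is never used as baseline, whether or not times are recorded.
2. Each post-dose value is the mean of its triplicate.
3. QTcF (Fridericia) is the primary correction for conclusions; any other correction is a sensitivity analysis only. Replace the sentence that leaves the choice open.

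Align the matching sentence in Protocol Section 14.5.1 so that the two documents agree. Items 1 and 2 need only a few SAP lines and the corresponding programming. Item 3 also touches the protocol, whose Section 15 requires changes to go through an amendment with IRB/IEC approval. No new data are needed.
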